Study 2: The RTM Protocol and Training feasibility study	To analyse the acceptability of the RTM Protocol among MH professionals and persons with PTSD and the adaptability of the RTM Protocol & RTM Training for the country context.	 Human participants  Vulnerable population  Human biological material  Pre-collected biological material  Personal data  Pre-collected personal data  risks on the environment  risks on the society

Please expand the rows in case of additional studies.

SECTION 4: DETAILS OF EACH STUDY

Study 1: The RTM Protocol Effectiveness Study

Target sample size: (Please justify the target sample size, either statistically or by referring to existing literature)	
The research sample for the EFFECTIVENESS STUDY is expected to be 120 participants (people with PTSD), approximately equally distributed between experimental and control groups (at least 20 participants).
 
The sample expectancy is based on case numbers estimated by every MH care provider involved in the Project. The allocation ratio was calculated based on the assumption that the mean of PCL-5 would be 25.0 for the control group and 21.0 for the experimental group (SD of 3.0); a type 1 risk is 5.0%, and a type 2 risk is 20.0%, for the bilateral test and a dropout rate at 20.0%, the minimum N of participants in each group should be equal to 12.

Key inclusion criteria:	Key inclusion criteria for the effectiveness study participants are (1) being adults \geq 18 years, (2) having a diagnosis of PTSD determined by DSM-5-TR or ICD-11 and/or (3) having PTSD symptoms causing clinically significant distress or impact on social, occupational, or other areas of functioning defining on base of using PTSD Checklist PCL-5, (4) being resident of Ukraine.
Key exclusion criteria:	Key exclusion criteria for the effectiveness study participants are (1) having any other acute comorbid mental health conditions, (2) receiving any other parallel PTSD treatment, (3) being unable to provide informed consent, has severe cognitive impairment, or is otherwise unlikely to adhere to study procedures.
Age range of participants:	Adults aged 18-65.
Country/ies of recruitment:	Ukraine

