Expected duration of procedure:	Data collection will occur at baseline (diagnostic session), 1 month after complete treatment application, in 6 months (follow-up booster session), and in 12 months (second follow-up booster session) and will take approximately 15 min each, 45 min per person.
Data Collection:	
Paper questionnaires, digital entry; no audio/video.
 
Data on age, gender, veteran and IDP statuses, residency, type of trauma, medical diagnosis and symptoms, scores from PCL-5 (for PTSD), PHQ-9 (for depression), GAD-7 (for anxiety) diagnostic scales will be collected from printed questionnaire sheets filled in by participants.
 
PTSD diagnosis will be collected from medical records.
 
Names, email-address, phone number will be collected from printed informed consent.
 
Data transfer. Aggregated, fully anonymised raw data will be shared by implementing partners' coordinators through Zenodo under closed access and using the EUSurvey Platform (an online survey-management

	
system developed by the European Commission) only with PI [name].

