Methodology:	
Research design. The RTM Protocol effectiveness study implies a randomised field trial comparing RTM with treatment-as-usual (TF-CBT, EMDR or pharmacotherapy). It is chosen and will be standardised based on CONSORT 2010 Statement: reporting parallel group randomised trials. To enhance the external validity of the findings, all the interventions are planned to be explored among three different settings of mental health care accustomed to Ukraine: mental health hospital care (inpatient and outpatient care for veterans) and psychotherapeutic practice (for civil trauma survivors).
 
Measures. Primary outcome effectiveness measures are MH professional proved existence or loss of PTSD diagnosis and/or PTSD symptoms severity measured by PTSD Checklist PCL-5 (re-experiencing of trauma, avoidance of trauma-related stimulus, negative alterations in cognition and mood, hyper-arousal).
 
Among secondary outcome measures will be the existence and severity of depression and anxiety-related symptoms according to PHQ-9 and GAD-7 scales.
 
Data analysis. Descriptive Statistics: means, SDs, medians, frequencies and percentages, baseline comparability between groups (t-tests, chi-square tests). Primary and Secondary Outcome Analysis: mixed-effects repeated measures ANOVA. Handling Missing Data: multiple imputation or maximum likelihood estimation under MAR assumption. Effect Size Reporting: Cohen's d, odds ratios, and 95% confidence intervals.
 
Data collection will be in Ukrainian language (all the scales are validated in Ukrainian and recommended by the World Health Organisation for the screening of the mentioned mental health conditions) at baseline (diagnostic session), 1 month after complete treatment application, in 6 months (follow-up booster session), and in 12 months (second follow-up booster session).

Study 2: The RTM Protocol and Training Feasibility Study

Target sample size: (Please justify the target sample size, either statistically or by referring to existing literature)	
The research sample for the FEASIBILITY STUDY is expected to be 20 participants according to the trauma-related cases/workforce availability ratio of implementing partners: 10 persons from each site.
 
The number of clients is expected to be 60 persons (persons treated with the RTM Protocol) according to the RTM Protocol effectiveness study description.

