
Pseudonymisation and Coding Strategy will be based on the European Data Protection Board (EDPB) Guidelines on Pseudonymisation, 2025.

The study design requires pseudonymisation only for follow-up post-treatment assessments for PTSD symptoms severity (PCL-5), existence and severity of depression (PHQ-9), and anxiety-related (GAD-7) symptoms at 2 weeks, 6 months, and 12 months post-treatment. The main purpose is to enable linkage of repeated assessments while restricting direct identification.

It is planned to have 3 experimental groups in 3 different treatment settings (Hospital Inpatient, Hospital Outpatient, Psychotherapeutic Practice) and 3 control groups with "treatment-as-usual" in the same three types of settings, with 20 participants each. It creates 6 study samples with 120 participants in total. Each participant will receive a unique study participant ID (PID) upon inclusion, generated as: [GroupCode]- [SettingCode]- [SequentialNumber]. For example, ExpHIP001: Experimental group, Hospital Inpatient setting, Participant 1.

Enrolment and randomisation (steps taken at baseline and immediately after each enrolment). As soon as a participant is enrolled, the site coordinator assigns a sequential number, allocates the study sample using Randomisation Software, and creates a PID. The coordinator writes down the PID on each paper document for follow-up contact and records the PID on the pseudonymization key list uploaded to the NPA/ RCFG staff laptop/desktop (encrypted hard drives).

Data collection (before and during follow-up assessments). Whenever data are gathered later, the research staff involved (therapists, assessors, or other professionals) manually write each participant's PID on every paper document related to that follow-up contact, allowing the data to be linked back to the correct person without revealing their identity.

For the follow-up post-treatment assessments (2 weeks / 6 months / 12 months), sites' coordinators will use the secure key to retrieve participant contact from the PID. Re-assessment tools will be administered with the same PID. Results will be stored again using a pseudonym only.

Study 2: The RTM Protocol and Training Feasibility Study

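### The repeated-measures ANOVA named for PCL-5, PHQ-9 and GAD-7 assumes, in its usual form, equal variances and correlations across unequally spaced visits; a model with unstructured covariance should replace it.

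*Protocol*

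**What the plan says.** Section 4 of the protocol, Study 1, Methodology (Data analysis) names one method for all primary and secondary scale outcomes, followed directly by the handling of missing values: "mixed-effects repeated measures ANOVA. Handling Missing Data: multiple imputation or maximum likelihood estimation under MAR assumption". The protocol states no covariance structure, sphericity correction or visit-specific error term.

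After baseline, the same section places the assessments at "1 month after complete treatment application, in 6 months (follow-up booster session), and in 12 months (second follow-up booster session". Section 6 instead gives the follow-ups as "at 2 weeks, 6 months, and 12 months post-treatment". On either reading the visits are unequally spaced.

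The short summary in Section 2 describes the symptom part of the primary outcome as a change, and lists the secondary outcomes at post-treatment, 6 and 12 months. No primary visit or exact contrast is defined. The sample-size paragraph assumes "the mean of PCL-5 would be 25.0 for the control group and 21.0 for the experimental group (SD of 3.0"), that is, one SD for PCL-5 and no correlation between visits.

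**The concern.** A classical repeated-measures ANOVA tests within-person effects against one pooled error term. That is valid if all pairwise differences between visits have the same variance (sphericity). The random-intercept mixed model that reproduces it imposes the stronger condition of equal variances and equal correlations (compound symmetry).

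With gaps ranging from weeks to six months, and a course of treatment between baseline and the first follow-up, equal correlation is hard to defend. The pooled term is then an average that may fit no single contrast. Choosing maximum likelihood for the missing data does not repair a covariance that is wrongly specified.

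The same line governs the primary scale and both secondary scales. What is at stake is the error rate of the group-by-time test and, more so, the intervals and tests for change at individual visits, including the long-term result at 12 months.

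**Working it through.** **Inputs from the protocol.** Six samples of 20 give 120 people, about 60 per arm. With 20% dropout, 60 × 0.8 = 48 per arm are evaluable, 96 in all. There are four assessments.

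**The plan's own figure.** For a difference of 4, SD 3, two-sided 5% and 80% power: n = 2 × (1.96 + 0.84)² × 3² / 4² = 8.8, so 9 per group, and 9 / 0.8 = 11.25, so 12. This agrees with "the minimum N of participants in each group should be equal to 12". It is a two-mean calculation and does not depend on the present point.

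**Inputs that must be assumed.** Correlations between visits and SDs by visit. Base case: visits at 0, 2, 8 and 14 months from baseline, correlation φ^|gap in months| with φ = 0.85, 0.90 or 0.95, SDs set to 1.

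**Formulas.** In large samples the pooled model uses the mean variance v and the mean covariance c of the true visit covariance S.
- Change from baseline to visit j: SE ratio (pooled / correct) = √[2(v − c) / (S00 + Sjj − 2·S0j)].
- Arm difference at visit j: SE ratio = √(v / Sjj).
- Actual two-sided error = 2 × [1 − Φ(1.96 × ratio)].

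**Worked case, φ = 0.85, equal SDs.** The six correlations are 0.7225, 0.2725, 0.1028, 0.3771, 0.1422 and 0.3771; their mean is 0.332, so 2(v − c) = 1.335.
- 12 months: true variance of change 2(1 − 0.1028) = 1.794; ratio √(1.335 / 1.794) = 0.863; error 9.1%.
- First follow-up: 2(1 − 0.7225) = 0.555; ratio √(1.335 / 0.555) = 1.55; error 0.2%.

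| φ | 12 months: ratio, error | First follow-up: ratio, error |
|---|---|---|
| 0.85 | 0.863, 9.1% | 1.55, 0.2% |
| 0.90 | 0.830, 10.4% | 1.67, 0.1% |
| 0.95 | 0.794, 12.0% | 1.82, under 0.1% |

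Simulation of 15,000 null trials per scenario, with 48 per arm, agrees: 9.0%, 10.3% and 12.0% at 12 months; 0.3%, 0.1% and 0.0% at the first follow-up. The group-by-time F test rejected in 6.2% to 7.0%. Repeat calculations vary a little, so I carry forward about 6% to 7.5%.

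**Smaller baseline SD (0.7 of the later SD).** For φ = 0.85: v = (0.49 + 3) / 4 = 0.8725, c = 0.2775, 2(v − c) = 1.190. The true 12-month variance of change is 0.49 + 1 − 2 × 0.7 × 0.1028 = 1.346. The ratio is 0.940 and the error 6.5%. Simulation over the three φ values gives 6.5%, 7.6% and 9.0%.

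**Other schedules, decaying correlation, equal SDs.** With visits at 0, 1, 6 and 12 months and a 6-month correlation of 0.5 to 0.8, the ratio is 2.15 to 2.44 at the first follow-up and 0.82 to 0.78 at 12 months (error 11% to 13%). Moving the first follow-up to half a month gives 2.99 to 3.44, with 12 months unchanged.

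**Patterns that break the direction.**
- True compound symmetry: all ratios 1.00, no error.
- Baseline correlates 0.3 with every later visit, and later visits correlate 0.7 with each other: c = 0.5, ratio √(1.0 / 1.4) = 0.85 at all three follow-ups, so the first follow-up is also too narrow.
- Decay with a 6-month correlation of 0.7 and SDs 1 / 2 / 1.4 / 1: 1.10 at the first follow-up and 1.21 at 12 months, both too wide.
- Arm difference at a visit with equal SDs: v = Sjj, ratio 1.00 whatever the correlations.
- Arm difference at a visit, the same decay, SDs 1 / 1.3 / 1.1 / 1: 0.85 at the first follow-up and 1.11 at 12 months.

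With an unstructured covariance the ratio is 1.00 in large samples in every one of these cases.

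**The case against.** The strongest reply is that the protocol never states a pooled error term. The label includes mixed effects, and maximum likelihood is one of the two missing-data options, so an unstructured fit would be compatible with the text. Covariance structure and degrees of freedom are often left to a SAP, which is not at hand. This stands to the extent that the point must be conditional on how the model is fitted. It does not remove the point: the protocol names a method, that method's usual form pools the error, and the alternative missing-data option, multiple imputation, can just as well be followed by a classical ANOVA.

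A reader might infer that the 12-month interval will be too narrow and the first follow-up interval too wide. The documents do not support that as a certainty. It needs a compound-symmetry fit, decaying correlation with roughly constant SDs, and a change-from-baseline contrast. The protocol fixes none of these, and the counter-cases above show the direction changing or the error vanishing.

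A reader might also take baseline scores to be truncated by the entry criteria. Section 4 admits people by diagnosis and/or PCL-5-based symptoms and states no cut-off, so truncation is not documented. The smaller baseline SD is only a sensitivity case, and it reduces the 12-month error.

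Finally, the test that an ANOVA delivers directly, group-by-time, is only mildly affected. That is correct and limits the weight of the point.

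**Conclusion.** The point holds in conditional form. If the named ANOVA is fitted in its usual form and visits are not equally correlated, the group-by-time test runs at about 6% to 7.5% instead of 5%, and single-visit change contrasts have wrong standard errors. Under decaying correlation and roughly constant SDs, the 12-month change test runs at about 9% to 12% with equal SDs, or 6.5% to 9% with a baseline SD of 0.7, while the first follow-up test rejects in 0.3% or less of null trials and so loses power. Arm differences at a visit with equal SDs are unaffected.

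All these sizes rest on assumed correlations, SDs and visit times. The case for changing the text does not depend on the direction, because an unstructured covariance is right in large samples under every pattern tried. The change should be made; the point does not undermine the design or the sample size.

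**What to change.** In Section 4, Study 1, Data analysis, replace the named ANOVA for PCL-5, PHQ-9 and GAD-7 by a mixed model for repeated measures: visit as a category, arm, arm-by-visit, unstructured within-person covariance, Kenward-Roger degrees of freedom, and arm differences with 95% confidence intervals estimated at each visit. If an ANOVA table is kept, use Greenhouse-Geisser-corrected tests and visit-specific error terms.

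The cost is one sentence, with the same data and standard software. Four visits need 4 × 5 / 2 = 10 covariance parameters, which about 96 evaluable people can support. Separately, the two statements of the first follow-up (1 month in Section 4, 2 weeks in Section 6) must be reconciled so that the visit categories are defined.

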Key inclusion criteria:	
Key inclusion criteria for MH professionals are (1) holding an accomplished higher education degree in the mental health area (psychology, psychiatry, psychiatric nursing, clinical social work), (2) having at least three years of hands-on clinical experience in mental-health settings, (3) being formally trained to deliver mental health care

	
to people exposed to trauma through accredited coursework, supervised practice, or equivalent, (4) meeting Ukrainian licensing and registration requirements mandated by health-care regulations and the implementing organisation's internal policies, (5) committing to attend the full training, complete all associated supervision sessions, and deliver the Protocol as specified by the study timeline.
 
The client sample is the same as for the study 1.

Key exclusion criteria:	
Key exclusion criteria for MH professionals are (1) being under investigation, suspension, or other disciplinary action by a professional body or employer, (2) lacking mandatory professional continuing education for the last year (min 40 hours), (3) having caseload exceeding the threshold for service quality requirements (> 30 active therapy clients).
 
The client sample is the same as for the study 1.

Age range of participants:	
Adults aged 18-65 (with regard to the eligibility criteria).
 
The same sample as for the study 1.

Country/ies of recruitment:	
Ukraine

Expected duration of procedure:	
MH Professional will be engaged into case statistic collection (30 min per case, 1 hour per person); satisfaction surveying (15 min per person) and focus-group interviews (1,5 hour of group work).
 
Clients will be engaged into satisfaction surveying (15 min per person).

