We also commit to transparency in dissemination: all publications will include clear disclaimers about the scope and limitations of the data, and no data will be shared with third parties outside the research consortium.

Data storage

	Raw data (incl. video or audio recordings)	Processed data (anonymized, pseudonymized)	Document(s) containing the names, contact information and personal details (the pseudonymisation key list)	Other material
Data carrier (digitalized or paper form)	Paper questionnaires Focus-group interview audio-recordings.	Excel files with fully anonymised data exported from EUSurvey Platform Word files with fully anonymised data transcribed from focus-group interview audio-recordings.	Informed consent forms, pseudonymization key list.	
Number of copies	Paper questionnaires for each client, 120 copies; for each MH professional, 40 copies. Focus-group interview audio-recordings, 1 copy for each implementing partner.	Numbers required by the needs of analysis, 1 copy for each type of data.	Informed consent forms for each client, 120 copies; for each MH professional, 40 copies. Pseudonymization key list, 1 copy for each site.	
Storage Location	Paper questionnaires are stored in locked cabinets at the sites' locations in Ukraine. Focus-group interview audio-recordings are stored locally on encrypted hard drives of implementing partners.	EUSurvey Platform (for data collection); ATLAS server (for data analysis and storage); Repository Zenodo (under closed access for data transferring; under open-access repository for open-access publications); Repository ORBilu (for open-access publications)	Informed consent forms are stored in locked cabinets at the sites' locations. Pseudonymization key lists are stored locally on encrypted hard drives of implementing partners.	
Retention period	Paper questionnaires will be destroyed after digital entry.	on EUSurvey Platform for 1 year; on ATLAS for up to 10 years; on Zenodo for the repository's lifetime, on ORBilu for the repository's lifetime.	Identifying data will be deleted 5 years following end of research project.	

Data access

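### Study 1 specifies no treating-professional code, so therapist clustering could not be modelled from the transferred data; intervals may be modestly too narrow

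*Protocol*

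**What the plan says.** All references are to the protocol; no SAP is at hand.

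- **Professionals.** Section 4, Study 2, Target sample size: the sample is "expected to be 20 participants according to the trauma-related cases/workforce availability ratio of implementing partners: 10 persons from each site". The inclusion criteria require these professionals to commit to delivering the RTM Protocol.
- **RTM clients.** Same entry: "The number of clients is expected to be 60 persons (persons treated with the RTM Protocol". This is the RTM half of the 120 participants in Study 1.
- **Other figures on caseload.** Study 2, Expected duration of procedure, plans "case statistic collection (30 min per case, 1 hour per person". The data storage table in Section 6 lists "Informed consent forms for each client, 120 copies; for each MH professional, 40 copies".
- **Participant ID.** Section 6, Study 1: "Each participant will receive a unique study participant ID (PID) upon inclusion, generated as: [GroupCode]- [SettingCode]- [SequentialNumber". It has no therapist element.
- **Client record.** Section 4, Study 1, Data Collection lists demographics, trauma type, diagnosis and symptoms, PCL-5, PHQ-9, GAD-7 and contact details. It does not list the treating professional.
- **Transfer.** Section 6, Study 1 gives the principal investigator access only to aggregated, anonymised data. Paper questionnaires are destroyed after digital entry.
- **Analysis.** Section 4, Study 1: "Primary and Secondary Outcome Analysis: mixed-effects repeated measures ANOVA". No random effects are named.

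The protocol does not say who delivers treatment-as-usual, or whether the same professionals treat both arms.

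**The concern.** Clients treated by the same professional share that person's skill and style. They may also share that person's way of judging outcome, because the primary outcome includes a professional's judgement of whether the PTSD diagnosis persists, and the professionals involved collect the clients' scales. If outcomes are positively correlated within therapist and each therapist works in one arm only, an analysis that treats clients as independent understates the standard error of the arm difference. The interval is then too narrow and the type I error exceeds 5%.

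Choosing random effects can be left to the SAP. Capturing the variable cannot: an SAP can name a therapist term, but the analyst can fit it only if the code was recorded at the site and survives anonymisation. The protocol fixes the ID structure and the list of data, and neither holds the code.

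**Working it through.** **1. The plan's own sample size.** Inputs from Section 4, Study 1: PCL-5 means 25.0 and 21.0 (difference 4.0), SD 3.0, two-sided 5%, power 80%, dropout 20%.

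n per group = 2 × [3.0 × (1.960 + 0.842) / 4.0]² = 8.83, rounded up to 9. With dropout, 9 / 0.80 = 11.25, rounded up to 12. The stated minimum of 12 is reproduced. The formula treats participants as independent.

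**2. Clients per professional (m), RTM arm.**

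- Study 2 sample sizes: 60 / 20 = 3.
- Time budget: 1 hour / 30 min per case = 2.
- If the 40 copies mean 40 professionals: 60 / 40 = 1.5. If they mean two copies for each of 20 professionals, m stays at 3.

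**3. Inflation of the standard error.** The ICC is an assumption, with range 0.05 to 0.15.

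- Design effect: DE = 1 + (m − 1) × ICC.
- True/naive SE, both arms clustered alike and therapists nested in arm: √DE.
- True/naive SE, only the RTM arm clustered: √[(DE + 1) / 2].
- True type I error of a nominal 5% test: 2 × [1 − Φ(1.96 / SE ratio)].

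Example, m = 3 and ICC 0.05: DE = 1 + 2 × 0.05 = 1.10. The SE ratio is √1.10 = 1.049 (both arms) or √1.05 = 1.025 (RTM only).

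| m | ICC | DE | SE ratio, RTM only | True alpha | SE ratio, both arms | True alpha |
|---|---|---|---|---|---|---|
| 3 | 0.05 | 1.10 | 1.025 | 5.6% | 1.049 | 6.2% |
| 3 | 0.10 | 1.20 | 1.049 | 6.2% | 1.095 | 7.4% |
| 3 | 0.15 | 1.30 | 1.072 | 6.8% | 1.140 | 8.6% |
| 2 | 0.05 | 1.05 | 1.012 | 5.3% | 1.025 | 5.6% |
| 2 | 0.15 | 1.15 | 1.037 | 5.9% | 1.072 | 6.8% |
| 1.5 | 0.05 | 1.025 | 1.006 | 5.1% | 1.012 | 5.3% |
| 1.5 | 0.15 | 1.075 | 1.019 | 5.4% | 1.037 | 5.9% |

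**4. Effect on the sample size.** Applying DE to both arms at m = 3: ICC 0.05 gives 9 × 1.10 / 0.80 = 12.4, so 13 per group; ICC 0.10 gives 13.5, so 14; ICC 0.20 gives 15.75, so 16. All lie below the planned 20 per group.

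**The case against.** **It belongs to the SAP.** A mixed model is already planned, and its random effects may be set later. That is true of the model term. It does not supply the variable, so this part stands only in part.

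**Absence is inferred from silence.** The data list describes mainly what participants enter on questionnaires and need not be the full record. The ID is a linkage key, and nothing bars a therapist field. The professionals collect the client data themselves, medical records exist at the sites, and identifying data, which the storage table groups with the key list, are kept for 5 years after the project ends. Site coordinators could probably restore the link. This stands: a reader might infer that clustering can never be modelled, and the documents do not support that. They support only that it cannot be modelled from the transferred data as now specified.

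**Harm is not certain.** A reader might also infer that the intervals are bound to be too narrow. That needs a positive ICC, which the documents do not give, and therapists nested in arm, which they do not state. If the same professionals treat both arms, ignoring the therapist main effect does not narrow the interval for the arm difference; only therapist-by-treatment variation would. This stands, and the conclusion is conditional for that reason.

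**The count of professionals is clerical.** The figure of 40 is a number of form copies, not a headcount. This stands too: it is a query to reconcile and does not by itself support the clustering point.

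**The code has a cost for anonymity.** With about 20 professionals, whose occupation and workplace are also transferred under Study 2, a therapist code on client records needs a check against the anonymisation commitment. A random intercept on 1.5 to 3 clients per therapist, before dropout, may also be poorly estimated. Both points stand and are taken into the fix.

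**Conclusion.** The point holds in a limited form. The Study 1 data as specified carry no treating-professional code, although about 20 professionals are expected to treat 60 RTM clients. Therapist clustering therefore could not be examined or modelled from the file that reaches the analyst, and an SAP alone cannot change that.

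The likely consequence is modest. It rests on three assumptions that the documents do not settle: an ICC of 0.05 to 0.15, an even spread of clients over professionals, and therapists nested in arm. At 3 clients each, the true SE exceeds the naive SE by about 2.5 to 7% and true alpha is 5.6 to 6.8% if only the RTM arm is clustered; the figures are 5 to 14% and 6.2 to 8.6% if both arms are. At 1.5 to 2 clients each, true alpha is 5.1 to 5.9% and 5.3 to 6.8% respectively. The issue is the validity of the intervals, not the number of participants.

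**What to change.** Before data collection:

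1. Add a coded, non-identifying therapist field to every Study 1 record in both arms, and keep it in the file transferred for analysis. It need not be part of the participant ID.
2. State whether the same professionals treat both arms.
3. Include a therapist random effect in the planned mixed model. If it is poorly estimated, use cluster-robust standard errors as a sensitivity analysis.
4. State one number of professionals, so that the Study 2 sample size, the time per case and the copy counts in the storage table agree.

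The cost is one extra field, slightly wider intervals, and a check that the code, combined with the occupation and workplace data of Study 2, does not undermine anonymisation.

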Methodology:	
Research design. The RTM Protocol and Training feasibility study will evaluate the RTM Protocol acceptability and adaptability during training and practice through case statistics, satisfaction surveying of MH practitioners and clients, and focus-group interviews with MH practitioners. As a standardisation base for the feasibility study the Framework for the development and evaluation of complex interventions issued by the National Institute for Health and Care Research (NIHR) was chosen.
 
Measures. To assess the RTM Protocol's acceptability by MH professionals, case statistics such as the number of trauma-related requests, trauma-specific cases treated with the RTM, hours spent for each case treatment, etc., will be collected. The standardised Intervention Usability Scale will also be applied.
 
Also, satisfaction with the procedure and therapeutic process from both sides (clients and MH professionals) will be surveyed regarding process comfort, expected and reached results, usefulness for different types of trauma and trauma-related symptoms, etc.
 
MH professionals' feedback will also be considered during the focus-group analysis. The focus-group protocol and script will be developed with input from every implementing partner to match the local frame of mental health care. The script previews topics such as the RTM Protocol use features, the RTM Protocol implementation benefits and challenges, the RTM Protocol effects and consequences, the RTM Protocol clients' acceptance and perception, etc.
 
The RTM Protocol's adaptability will be measured by analysing the case statistics and MH professionals' feedback for the Ukrainian version of the protocol.
 
Data analysis. For Quantitative Analysis will be utilised descriptive statistics (frequencies, means, SDs for usability and satisfaction scores), correlation analysis (between usability scores and satisfaction or case outcomes (e.g., Spearman's rho)).
 
Qualitative Analysis will be conducted using thematic analysis (transcripts coded using inductive and deductive approaches, themes mapped to NIHR framework domains), charting and mapping.

SECTION 5: RISK ASSESSMENT AND RISK MINIMIZATION

Study 1: The RTM Protocol Effectiveness Study

Potential risk(s)	Extent of risk(s) and measures taken

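### The raw count of cases treated with RTM, listed as a measure of professionals' acceptability, mostly reflects randomised allocation and enrolment; delivery out of allocation, with reasons, would be the informative measure.

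*Protocol*

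**What the plan says.** Study 2 has professionals' acceptability of RTM as part of its first objective. The Protocol, Section 4, Study 2, Methodology (Measures), names the data for it: "acceptability by MH professionals, case statistics such as the number of trauma-related requests, trauma-specific cases treated with the RTM", together with hours per case and other items. The Intervention Usability Scale, satisfaction surveys and focus groups are added. The same section also uses the case statistics for adaptability.

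The RTM clients come from the randomised trial. Under Target sample size for Study 2: "The number of clients is expected to be 60 persons (persons treated with the RTM Protocol) according to the RTM Protocol effectiveness study description". Under the eligibility criteria for Study 2: "The client sample is the same as for the study 1".

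In that trial the treating professional does not choose the arm. Section 6, Study 1, says that the site coordinator "allocates the study sample using Randomisation Software, and creates a PID". The plan is three RTM groups and three control groups "in the same three types of settings, with 20 participants each". Professionals are eligible for Study 2 only if, among other things, they commit to "deliver the Protocol as specified by the study timeline".

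**The concern.** A count of cases treated shows acceptance when the professional is free to use the method or leave it. For randomised clients that freedom is largely absent. Software decides who is assigned to RTM, and the professional has agreed beforehand to deliver it. A count near 60 would then mainly say that the trial recruited and allocated as planned.

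What is at stake is the meaning of one item among several under the acceptability objective. A high count could be presented as good acceptance when it is planned exposure. A low count could be presented as poor acceptance when the cause is slow enrolment or clients leaving. Because the case statistics also serve the adaptability objective, the same ambiguity reaches that one.

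**Working it through.** **Inputs**
- RTM groups: 3, control groups: 3, each of 20 (Section 6, Study 1).
- RTM clients in Study 2: 60 (Section 4, Study 2, Target sample size).
- Professionals: 20, as 10 from each of two partners (same place).
- Dropout assumed for Study 1: 20% (Section 4, Study 1, Target sample size).

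**Step 1: reproduce the plan's figure.** RTM cases = 3 x 20 = 60, which matches the stated 60. Total = 6 x 20 = 120. RTM share = 60/120 = 50%. Spread over 20 professionals, the average is 60/20 = 3 RTM cases each. The Protocol does not say how clients are divided among professionals, so only the average follows.

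**Step 2: what sets the count among trial clients.** Cases delivered = clients enrolled x share allocated to RTM x share of allocated clients in whom RTM is delivered.
- The first factor is recruitment.
- The second is the randomisation. Groups of 20 fix it at one half. If allocation were instead simple 1:1 randomisation (an assumption, since the method is not described), the number allocated to RTM out of 120 would have SD = sqrt(120 x 0.5 x 0.5) = 5.5 and a 95% range of about 49 to 71 by chance alone.
- Only the third factor can be moved by a professional's view of RTM. It is also moved by clients who leave.

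**Step 3: can the raw count isolate the third factor?** Take an observed count of 48. It fits at least three situations:

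| Situation | Allocated | Delivered | Professional-initiated non-delivery |
|---|---|---|---|
| Enrolment reaches 80% of plan (96 clients), all RTM delivered | 48 | 48 | 0 |
| Full enrolment, 20% of RTM clients leave | 60 | 60 x 0.8 = 48 | 0 |
| Full enrolment, professionals do not deliver in 20% | 60 | 60 x 0.8 = 48 | 12 |

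The 20% is the dropout assumption of Study 1, used here only as an illustration of non-delivery. Dividing by the number allocated separates the first row (48/48 = 100%) from the other two (48/60 = 80%). It does not separate the second from the third: professional-initiated non-delivery could be anywhere from 0/60 to 12/60, that is 0% to 20%. For that, the decision-maker and the reason are needed.

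**Step 4: are those data planned?** The denominator is available, because each participant ID carries the group code (Section 6, Study 1). The case-statistics items listed in Section 4, Study 2, Data Collection cover requests, RTM cases, hours, comfort, results and usefulness. They do not include start, completion, stopping, decision-maker or reason. Paper sheets are destroyed after entry and the principal investigator receives only aggregated, anonymised data (Section 6), so an item not captured at the time would be hard to recover.

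**The case against.** The other side has four fair arguments.

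1. **Randomisation fixes allocation, not delivery.** The item is cases treated. Clients can drop out, the safety section provides for terminating the intervention, and a commitment at entry is not proof of delivery. This stands. A reader might infer that the count would be identical whether professionals like or dislike RTM. The documents do not support that, since dislike could show as a shortfall. What remains is that the raw count does not reveal the cause of a shortfall.

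2. **No misuse is planned.** The Protocol defines no ratio of RTM cases to requests, no threshold and no comparison of counts between professionals or sites. The quantitative analysis it describes concerns usability and satisfaction scores and their correlations. This stands too, and further detail may sit in an analysis plan that is not shown. The Protocol nevertheless states the purpose for which the count is collected, and for randomised clients that purpose fits poorly.

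3. **The case sheet may reach beyond the trial.** Requests, and an evaluation covering training and practice, could refer to a professional's whole caseload, where discretion exists. No sentence limits the sheet to trial clients. Equally, none says that RTM cases outside the trial are counted, and the stated client sample is that of Study 1. The scope is open and needs a sentence.

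4. **The objective has other measures.** The usability scale, satisfaction surveys, hours per case and focus groups are not set by randomisation. This stands in full and limits the weight of the point.

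**Conclusion.** The point holds in a limited form. For the Study 1 clients, the raw number treated with RTM is mainly a measure of exposure: 60 of 120 by plan, about 3 per professional on average. Whatever it can say about acceptability lies in the gap between allocated and delivered cases, and the raw count mixes professionals' decisions with client dropout. With a 20% gap taken as an illustration, the professional-initiated part is unknown between 0 and 12 of 60.

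This rests on two readings: that the RTM cases counted are the Study 1 clients, as the sample statements suggest, and that the listed case-statistics items are those on the sheet. If discretionary use outside the trial is also counted, that part could reflect choice, but only if it is shown apart.

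It would be a step too far to conclude that the acceptability objective fails, because its other measures are untouched. No sample size, primary outcome or Study 1 conclusion changes. It is a modest and inexpensive improvement, best made before data collection because the missing fields would be hard to reconstruct afterwards.

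**What to change.** In the Protocol, Section 4, Study 2 (Measures and Data Collection):

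- Describe the number of cases treated with RTM as descriptive exposure only.
- On the existing case sheet, record for each client allocated to RTM whether it was started, completed or stopped, by whose decision (professional, client or other) and why.
- Use started/allocated and completed/allocated as the acceptability indicator from case statistics. Show professional-initiated non-delivery separately from client dropout.
- State whether RTM use outside the randomised clients is counted. If it is, report it separately.

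**Cost:** two or three extra fields per RTM case and a few lines of wording, with no change to sample size, visits or treatment. The sheet must cover every client allocated to RTM. The time estimate for case statistics (30 minutes per case, 1 hour per person) can be read as 60/30 = 2 cases per professional, or 20 x 2 = 40 cases against 60 RTM clients, so it should be checked at the same time.
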